structural heart disease remain modest. Five randomized clinical trials of VT ablation procedures have been performed [8-12] and are summarized in a recent meta-analysis [13]. Other large multi-center studies have been published which did not randomize catheter ablation against medical therapy but are nonetheless important when assessing the overall success rates of this therapy [14-17]. In the meta-analysis that included 457 participants with largely ischemic cardiomyopathy and mean left ventricular ejection fraction of 30-35%, the recurrence rate of VT was 35% (range 12-50%) with catheter ablation (n=266) during a follow up of 6-22 months. This compared favorably to a recurrence rate of 55% (range 33-75%) in the medical-only control group (n=191). In other large prospective observational studies, risk of VT recurrence at one year after extensive catheter ablation approaches 50% [14-17].

VT ablation procedures can “fail” for many reasons. Commonly cited limitations include: 1) inability to map hemodynamically unstable VT; 2) difficult mapping due to multiple different VT circuits; 3) inability to create necessary radiofrequency ablation due to depth of myocardial scar; 4) inability to reach the critical component of the VT circuit with a catheter; 5) protective structures (i.e., epicardial fat) around the critical component of the VT circuit; and 6) late development of new abnormal circuits through myocardial scar after the original ablation. Methods to improve the success of VT ablation procedures need to address these key limitations. Examples of alternative methods in development for enhanced tissue destruction include: 1) injection of alcohol into smaller blood vessels to induce larger myocardial infarction; 2) development of catheters with extendable needles to impale ventricular myocardium to allow deeper radiofrequency ablation; and 3) using two ablation catheters to encircle the critical component of the scar in hopes of deeper penetration of thermal energy.

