3.0 PATIENT SELECTION

3.1 Inclusion Criteria

1. DOCUMENTED VT:
 - a. Patient must have documented sustained monomorphic ventricular tachycardia as documented on either a 12-lead ECG or intracardiac ICD interrogation
 - OR—
 - b. Monomorphic PVCs documented on a 12-lead ECG.
2. ANTIARRHYTHMIC MEDICATION: Patient must have failed or become intolerant to at least one antiarrhythmic medication (amiodarone, sotalol, or mexiletine).
—AND—
3. CATHETER ABLATION: Patient must have failed at least one invasive catheter ablation procedure, or have a contraindication to a catheter ablation procedure (e.g., LV thrombus, severe pulmonary disease), or have VT thought to arise from a protected location (e.g., epicardial VT with history of previous cardiac surgery).
4. MINIMUM VT BURDEN: Patient must have either:
 - a. At least 3 VT episodes (sustained VT, ICD ATP or ICD shock) over previous 6 months prior to enrollment
 - OR—
 - b. >20% PVC burden with a cardiomyopathy (LVEF<50%)
5. Patient must be deemed medically fit for stereotactic body radiation therapy by the treating physician.
6. Patient must be \geq 18 years old.
7. Patient must be able to understand and be willing to sign an IRB approved written informed consent document.

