11.2 Sample Size Justification

A total of 19 patients will be enrolled, which provides an optimal balance between assuring a high likelihood of safety (Phase I) with a preliminary assessment of efficacy (Phase II).

For the phase I component, the baseline rate of SAEs for catheter ablation is assumed to be 10-15%. Given the population being studied and a reasonable expectation that patients may be at a higher than typical risk of toxicity from any salvage therapy, we assume that SAE rates up to 20% would be clinically acceptable. Having said that, given that this is a totally noninvasive technique, it may well be that rates of toxicity are lower than that expected with catheter ablation. After exploring patient ranges from 15-25 patients, it was determined that 19 patients would provide a 75.4% power to detect an SAE rate about 20% (range, 5%-20%, $\alpha = 0.0829$).

For the phase II component, while some single institution series report much higher success rates, the baseline efficacy rate of catheter ablation in prospective trials ranges from 50-65%. As this is a salvage therapy in a high risk population, we assume that efficacy rates as low as 40% would be clinically acceptable. Using the 19 patient sample determined above, it was determined that 19 patients would provide 81.5% power to determine that ENCORE is not worse than 40% effective for the treatment of VT (range, 40-65%, $\alpha = 0.0885$).

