11.3 Analytic Plan for Primary Objectives

SAEs defined by CTCAE v4.0 criteria within 90 days of ENCORE that are possibly/probably/definitely related to study treatment will be recorded. ENCORE therapy will be deemed safe if the rate of SAEs is $\leq 20\%$. An additional early stopping rule dictates that if 5 or more out of the first 10 patients develop ENCORE related SAEs, the trial will be halted.

The number of ICD therapies delivered in the 6 month periods preceding and following ENCORE therapy will be recorded for each patient by interrogation of the ICD. ENCORE therapy will be deemed efficacious if there is a reduction in ICD therapies before and after treatment. The proportion of patients with efficacious ENCORE therapy will be calculated, with the intent of demonstrating at least 40% efficacy.

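### In VT patients, reaching 40% with any reduction in ICD therapies does not by itself show efficacy: the bar matches a harder outcome, and the stated alpha is not the error rate under no effect

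*Combined protocol and SAP*

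**What the plan says.** Section 11.2 fixes the size of the single arm ("A total of 19 patients will be enrolled") and starts the efficacy benchmark from catheter ablation: "the baseline efficacy rate of catheter ablation in prospective trials ranges from 50-65" percent. It then lowers the benchmark for a salvage population: "we assume that efficacy rates as low as 40% would be clinically acceptable". The claimed operating characteristics are "81.5% power to determine that ENCORE is not worse than 40% effective for the treatment of VT (range, 40-65%, $\alpha = 0.0885". Efficacy is not defined there.

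Sections 2.1 and 11.3 define success for an ICD patient as any reduction in ATP and shocks between the six months before and the six months after treatment, with no minimum size. The trial-level criterion in 11.3 is "The proportion of patients with efficacious ENCORE therapy will be calculated, with the intent of demonstrating at least 40% efficacy"; no count cut-off is written.

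VT patients qualify under section 3.1 item 4a with "At least 3 VT episodes (sustained VT, ICD ATP or ICD shock) over previous 6 months prior to enrollment". Section 2.2 lists 50% and 95% reductions and shocks alone as secondary endpoints. Section 11.4 plans only descriptive statistics for efficacy and strict efficacy.

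**The concern.** The benchmark and the endpoint appear to measure different things. Section 1.2 says of catheter ablation that "the recurrence rate of VT was 35% (range 12-50%) with catheter ablation (n=266"), and puts one-year recurrence near 50% in observational series. The complements, 65% and 50%, are the two ends of the range in 11.2. A patient who goes from 30 therapies to 29 is a success here but a recurrence on the benchmark's scale.

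Patients are also selected for a recent burden of VT, and largely the same months serve as the comparator. With no control arm, ordinary fluctuation and regression from a high period count as response. If the no-effect response rate is above 40%, the stated alpha does not protect against the error that matters, and the 11.2 conclusion about effectiveness would not follow from a pass.

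**Working it through.** **1. The plan's own figures.** Inputs from 11.2: n = 19, null 40%, alternative 65%. For an exact one-sided binomial with success at 11 or more:

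- alpha = P(X ≥ 11 | 19, 0.40) = 0.0885 (stated 0.0885)
- power = P(X ≥ 11 | 19, 0.65) = 0.8145 (stated 81.5%)

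The design reproduces, so 11.2 implies a cut-off of 11/19. Read literally, 11.3 needs only 8/19, since 8/19 = 42.1% and 7/19 = 36.8%.

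**2. Source of the benchmark.** From 1.2: 1 − 0.35 = 0.65 and 1 − 0.50 = 0.50, matching 50-65%. That the range means freedom from recurrence is inferred from this match.

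**3. Response with no effect: an argument that needs little modelling.** Suppose the before and after counts are exchangeable and the before count is at least 3. Let s be the share of these patients with fewer than 3 therapies after; all of them are responders. Let t be the share of ties among the rest, whose non-tied pairs split evenly. Then

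P(any reduction) = s + (1 − s)(1 − t)/2.

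Even with s = 0, this falls below 0.40 only if t exceeds 0.20. In the simulations below, t was 0.04-0.17.

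**4. Response with no effect: simulation.** The documents give no count distribution, so this is assumed: patient rates Gamma (shape 0.5, 1 or 2; mean 4, 8 or 15 per 6 months), Poisson counts, equal 6-month windows, before count at least 3, and 500,000 patients per scenario before selection. In the fluctuating scenarios each window's rate has an independent Gamma multiplier (shape 1 or 2, mean 1).

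| Scenario | Any reduction | 95% reduction |
|---|---|---|
| Rate unchanged, stable | 0.48-0.55 | 0.00-0.03 |
| Rate unchanged, fluctuating | 0.54-0.71 | 0.04-0.21 |
| Rate up 25%, stable (means 4-30) | 0.19-0.40 | 0.00-0.02 |
| Rate up 25%, fluctuating (means 4-30) | 0.43-0.65 | 0.02-0.17 |

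A wider unchanged-rate grid (means 3-30, stronger clustering) gave 0.46-0.80 for any reduction and up to 0.39 for 95% reduction. If the six-week blanking period shortens the after window without a rate adjustment, that grid gives 0.61-0.85. That is a separate matter and is not counted here.

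**5. Chance of passing, n = 19.**

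| True response | P(≥ 11/19) | P(≥ 8/19) |
|---|---|---|
| 0.40 | 0.0885 | 0.51 |
| 0.48 | 0.26 | 0.77 |
| 0.50 | 0.32 | 0.82 |
| 0.60 | 0.67 | 0.96 |
| 0.70 | 0.92 | 0.997 |
| 0.71 | 0.93 | 0.998 |

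**6. A cut-off against a no-effect reference.** Keeping n = 19 and one-sided alpha at or below 0.0885:

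- Reference 0.50: 13/19 (alpha 0.0835), power 48% at 65%.
- Reference 0.60: 15/19 (alpha 0.0696).
- Reference 0.70: 17/19 (alpha 0.0462).

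**The case against.** **The no-effect rate is not known.** This stands. The models are assumed, and the unchanged-rate scenarios set aside features the documents mention: section 4.10 describes antiarrhythmic dose reductions after six weeks when no VT is seen, and section 5.1 expects heart failure to progress. If the underlying rate rises 25%, the stable-rate models fall to 0.40 or below. The highest pass probabilities need strong fluctuation between windows. Other features could push the other way, such as discretionary ICD programming (4.10) and early death, which shortens the period in which therapies can occur.

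**The simulated entry rule is not quite the protocol's.** This also stands. Item 4a counts sustained VT as well as ICD therapies and runs back from enrollment, whereas the comparator runs back from treatment. Some patients may enter with few therapies to reduce. The 19 may also include PVC patients, to whom this calculation does not apply.

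**The plan promises only preliminary efficacy, and calls 40% a clinical-acceptability judgement.** That justifies a small single arm. It does not turn 0.0885 into the chance that an ineffective treatment passes.

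**Three stronger readings that a reader might infer are not supported.**

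- *Phase II cannot show efficacy at all.* Even at a no-effect rate of 0.80, 19/19 has probability 0.8^19 = 0.014, so a near-unanimous result would inform.
- *The documents' own untreated patients already clear the bar.* Section 1.2 says "This compared favorably to a recurrence rate of 55% (range 33-75%) in the medical-only control group (n=191"), so 45% were recurrence-free. Those patients differ from this cohort: two of the trials are titled as prophylactic ablation or ablation before defibrillator implantation, while patients here have failed a drug and have failed, or are poorly suited to, ablation. The figure is context only. If it did transfer, a 40% bar on freedom from therapy would be undercut too, with P(≥ 11/19 | 0.45) = 0.18.
- *The primary endpoint must be replaced by zero therapy or 95% reduction.* That changes the estimand, and nothing in the documents supports 65% on such a measure in salvage patients.

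**Conclusion.** The concern holds in a limited form. The stated alpha of 0.0885 is correct against a true response of 40%, but it is not the probability that an ineffective treatment passes. With an unchanged underlying rate, about half or more of selected VT patients would be expected to show some reduction (0.48-0.71). The 11/19 rule then passes an ineffective treatment with probability about 0.26-0.93, and the literal 8/19 reading with probability about 0.77-0.998. Meeting 40% alone therefore does not support the effectiveness statement in 11.2.

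This rests on assumed count models, equal windows, no trend in the underlying rate, all 19 being VT patients, and the inference that 50-65% means freedom from recurrence. A worsening underlying rate would weaken it. The 95% reduction endpoint is much less exposed, at 0-0.21 in the main unchanged-rate models and up to 0.39 in the wider grid at low burden with strong clustering. The PVC rule was not assessed.

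**What to change.** Keep any reduction as the primary measure for VT patients, and change what is concluded from it:

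1. In 11.2 and 11.3, remove the inference that meeting 40% shows ENCORE to be no worse than 40% effective. State that the benchmark refers to a different outcome and that 0.0885 is not the error rate under no effect.
2. In 11.3, report the proportion with an exact confidence interval, read against a no-effect reference of at least 50%. For 19 VT patients the matching cut-off is 13/19 (one-sided alpha 0.0835, power 48% at 65%). If PVC patients are enrolled, use the number of VT patients as n and recompute the cut-off.
3. Base any efficacy statement jointly on any reduction and the 95% reduction endpoint in 2.2 item 5.

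This changes wording and analysis only. It uses the same ICD interrogations and needs no additional patients. The cost is a more cautious efficacy claim and lower stated power (48% rather than 81.5% at 65%).

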11.4 Analytic Plan for Secondary and Exploratory Objectives

Adverse events will be tabulated by type and grade.

Descriptive statistics will be used to describe efficacy and strict efficacy, changes in SF-36 scores, changes in ECGI, differences in purely ECGI derived vs. clinically-derived target volumes.

Dose-volume parameters to the ENCORE target as defined by ECGI and the clinical target volume will be correlated with the reduction in VT through descriptive statistics and Cox regression.

